## **7.3 Definitions of Adverse Events**

### **7.3.1 Adverse Event**

An adverse event (also known as an adverse experience) is defined as any untoward medical occurrence associated with the use of a drug in humans, whether or not considered drug related. More specifically, an adverse event (can be any unfavorable and unintended sign (e.g., an abnormal laboratory finding), symptom, or disease temporally associated with the use of a drug, without any judgment about causality. An adverse event can arise from any use of the drug (e.g., off-label use, use in combination with another drug) and from any route of administration, formulation, or dose, including an overdose.

### **7.3.2 Adverse reaction**

An adverse reaction is defined as any adverse event caused by the use of a drug. Adverse reactions are a subset of all suspected adverse reactions for which there is reason to conclude that the drug caused the event.

#### **7.3.2.1 Suspected**

A suspected adverse reaction is defined as any adverse event for which there is a reasonable possibility that the drug caused the adverse event. For the purposes of IND safety reporting, "reasonable possibility" indicates that there is evidence to suggest a causal relationship between the drug and the adverse event. A suspected adverse reaction implies a lesser degree of certainty about causality than an adverse reaction.

#### **7.3.2.2 Unexpected**

An adverse event or suspected adverse reaction is considered *unexpected* if it is not listed in the investigator brochure or package insert(s), or is not listed at the specificity or severity that has been observed, or, if an investigator brochure is not required or available, is not consistent with the risk information described in the general investigational plan or elsewhere in the current application.

“Unexpected,” as used in this definition, also refers to adverse events or suspected adverse reactions that are mentioned in the investigator brochure as occurring with a class of drugs or as anticipated from the pharmacological properties of the drug, but are not specifically mentioned as occurring with the particular drug under investigation.

Adverse events that would be anticipated to occur as part of the disease process are considered *unexpected* for the purposes of reporting because they would not be listed in the investigator brochure. For example, a certain number of non-acute deaths in a cancer trial would be anticipated as an outcome of the underlying disease, but such deaths would generally not be listed as a suspected adverse reaction in the investigator brochure.

Some adverse events are listed in the Investigator Brochure as occurring with the same class of drugs, or as anticipated from the pharmacological properties of the drug, even though they have not been observed with the drug under investigation. Such events would be considered *unexpected* until they have been observed with the drug under investigation. For example, although angioedema is anticipated to occur in some patients exposed to drugs in the ACE inhibitor class and angioedema would be described in the investigator brochure as a class effect, the first case of angioedema observed with the drug under investigation should be considered *unexpected* for reporting purposes.

### 7.3.2.3 Serious

An adverse event or suspected adverse reaction is considered *serious* if, in the view of either the investigator- sponsor, it results in any of the following outcomes:

- Death
- Life-threatening adverse event
- Inpatient hospitalization or prolongation of existing hospitalization
- A persistent or significant incapacity or substantial disruption of the ability to conduct normal life function
- Congenital anomaly/birth defect

Important medical events that may not result in death, are life-threatening, or require hospitalization may be considered serious when, based upon appropriate medical judgment, they may jeopardize the patient or subject and may require medical or surgical intervention to prevent one of the outcomes listed in this definition. Examples of such medical events include allergic bronchospasm requiring intensive treatment in an emergency room or at home, blood dyscrasias or convulsions that do not result in inpatient hospitalization, or the development of drug dependency or drug abuse.

### 7.3.2.4 Life-threatening

An adverse event or suspected adverse reaction is considered *life-threatening* if, in the view of either the investigator- sponsor, its occurrence places the patient or subject at immediate risk of death. It does not include an adverse event or suspected adverse reaction that, had it occurred in a more severe form, might have caused death.

## 7.4 Recording of an Adverse Event

All grade 3 and above adverse events will be entered into OnCore®, whether or not the event is believed to be associated with use of the study drug. Data about these events and their severity will be recorded using the NCI CTCAE v4.03.

The Investigator will assign attribution of the possible association of the event with use of the investigational drug, and this information will be entered into OnCore® using the classification system listed below:

| Relationship                            | Attribution | Description                                       |
|--|--------------------|--|
| Unrelated to investigational drug/intervention | Unrelated          | The AE is clearly NOT related to the intervention |
|  | Unlikely           | The AE is doubtfully related to the intervention  |
| Related to investigational drug/intervention   | Possible           | The AE may be related to the intervention         |
|  | Probable           | The AE is likely related to the intervention      |
|  | Definite           | The AE is clearly related to the intervention     |

Signs or symptoms reported as adverse events will be graded and recorded by the Investigator according to the CTCAE. When specific adverse events are not listed in the CTCAE they will be graded by the Investigator as *none*, *mild*, *moderate* or *severe* according to the following grades and definitions:

- Grade 0 No AE (or within normal limits)
- Grade 1 Mild; asymptomatic or mild symptoms; clinical or diagnostic observations only; intervention not indicated
- Grade 2 Moderate; minimal, local, or noninvasive intervention (e.g., packing, cautery) indicated; limiting age-appropriate instrumental activities of daily living (ADL)
- Grade 3: Severe or medically significant but not immediately life-threatening; hospitalization or prolongation of hospitalization indicated; disabling; limiting self-care ADL
- Grade 4: Life-threatening consequences; urgent intervention indicated
- Grade 5: Death related to AE

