## 7.6 Adverse Events Monitoring

All adverse events, whether or not unexpected, and whether or not considered to be associated with the use of the study drug, will be entered into OnCore®, as noted above.

The Investigator will assess all adverse events and determine reportability requirements to the UCSF Data and Safety Monitoring Committee (DSMC) and UCSF's Institutional Review Board (IRB); and, when the study is conducted under an Investigational New Drug Application (IND), to the Food and Drug Administration (FDA) if it meets the FDA reporting criteria.

All adverse events entered into OnCore® will be reviewed by the Helen Diller Family

Comprehensive Cancer Center Site Committee on a weekly basis. The Site Committee will

review and discuss at each weekly meeting the selected toxicity, the toxicity grade, and the attribution of relationship of the adverse event to the administration of the study drug(s).

All grade(s) 3-5 adverse events entered into OnCore® will be reviewed on a monthly basis at the Site Committee meetings. The Site Committee will review and discuss the selected toxicity, the toxicity grade, and the attribution of relationship of the adverse event to the administration of the study drug(s).

In addition, all suspected adverse reactions considered "serious" entered into OnCore®, will be reviewed and monitored by the Data and Safety Monitoring Committee on an ongoing basis and

discussed at DSMC meetings, which take place every six weeks.

For a detailed description of the Data and Safety Monitoring Plan for a Multicenter Phase 2 or 3 Institutional Study at the Helen Diller Comprehensive Cancer Center please refer Appendix 4 Multicenter Institutional Studies.

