## 9.6 Case Report Forms (CRFs)

The Principal Investigator, and/or his/her designee, will prepare and maintain adequate and accurate participant case histories with observations and data pertinent to the study. Study specific Case Report Forms (CRFs) will document safety and treatment outcomes for safety monitoring and data analysis. All study data will be entered into OnCore® via standardized CRFs in accordance with the CTMS study calendar, using single data entry with a secure access account. The Clinical Research Coordinator (CRC) will complete the CRFs as soon as possible upon completion of the study visit; the Investigator will review and approve the completed CRFs.

The information collected on CRFs shall be identical to that appearing in original source documents. Source documents will be found in the patient's medical records maintained by UCSF personnel. All source documentation should be kept in separate research folders for each patient.

In accordance with federal regulations, the Investigator is responsible for the accuracy and authenticity of all clinical and laboratory data entered onto CRFs. The PI will approve all completed CRFs to attest that the information contained on the CRFs is true and accurate.

All source documentation and CTMS data will be available for review/monitoring by the UCSF DSMC and regulatory agencies.

The Principal Investigator will be responsible for ensuring the accurate capture of study data. At study completion, when the CRFs have been declared to be complete and accurate, the database will be locked. Any changes to the data entered into the CRFs after that time can only be made by joint written agreement among the Study Chair, the Trial Statistician, and the Protocol Project Manager.

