### 3. Review and Oversight Requirements

#### 3.1 Adverse Event Monitoring

All Grade 3-5 Adverse Events (AEs), regardless of being unexpected or considered to be associated with the use of the study drug will be entered into OnCore®, UCSF's Clinical Trial Management System.

Adverse Events are graded according to the Common Terminology Criteria for Adverse Events (CTCAE) as developed and revised by the Common Therapy Evaluation Program (CTEP) of the National Cancer Institute. Adverse Events are further given an assignment of attribution or relationship to treatment or medical procedure. Attribution categories are:

- **Definite** – The adverse event is clearly related to the investigational agent(s) or medical procedure.
- **Probable** – The adverse event is likely related to the investigational agent(s) or medical procedure.
- **Possible** – The adverse event may be related to the investigational agent(s) or medical procedure.
- **Unlikely** – The adverse event is doubtfully related to the investigational agent(s) or medical procedure.
- **Unrelated** – the adverse event is clearly not related to the investigational agent(s) or medical procedure.

All Grade 3-5 adverse events entered into OnCore® will be reviewed on a monthly basis at the UCSF Site Committee meetings. All adverse events entered into OnCore® will be reviewed on a monthly basis at the UCSF Coordinating Center Site Committee meetings. All clinically significant adverse events must be reported to the UCSF Coordinating Center by the participating sites within 10 business days of becoming aware of the event or during the next scheduled monthly conference call, whichever is sooner. The UCSF Site Committee will review and discuss the selected toxicity, the toxicity grade, and the attribution of relationship of the adverse event to the administration of the study drug(s) from the UCSF Coordinating Center and the participating sites.

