#### 3.2 Serious Adverse Event Reporting

By definition, an Adverse Event is defined as a Serious Adverse Event (SAE) according to the following criteria:

- Death.
- Life-threatening (i.e. results in an immediate risk of death).
- Requires inpatient hospitalization or prolongation of existing hospitalization.
- Permanent or significant disability/incapacity.
- Gives rise to a congenital anomaly/birth defect, or cancer, or any experience that suggests a significant hazard, contraindication, side effect, or precaution that may require medical or surgical intervention to prevent one of the outcomes listed above.
- Event occurring in a gene therapy study.
- Event that changes the risk/benefit ratio of a study.
- Any other event the Principal Investigator judges to be serious or which would

suggest a significant hazard, contraindication, side effect, or precaution.

Serious Adverse Event reporting will be in accordance with the UCSF IRB Regulations and Code of Federal Regulation Title 21 Part 312.32. The SAE will be reported on a Med Watch form.

UCSF IRB website for guidance in reporting serious adverse events:

<https://irb.ucsf.edu/adverse-event>

FDA website for guidance in reporting serious adverse events:

[www.fda.gov/Safety/MedWatch/HowToReport/default.htm](http://www.fda.gov/Safety/MedWatch/HowToReport/default.htm)

Med Watch forms and information:

[www.fda.gov/medwatch/getforms.htm](http://www.fda.gov/medwatch/getforms.htm)

All Serious Adverse Events are entered into OnCore®, as well as submitted to the IRB (per IRB guidelines) via iRIS®. All SAEs, whether expected or unexpected, must be reported to the UCSF Coordinating Center within 1 business days of becoming aware of the event. The SAEs are reviewed and monitored by the UCSF Data and Safety Monitoring Committee on an ongoing basis and discussed at DSMC meetings, which take place every six weeks. The date the SAE was sent to all required reporting agencies will be documented in OnCore®.

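### Two sections set OnCore adverse event entry at Grade 3 and above and a third at all grades, while five of the nine safety endpoints draw on non-serious Grade 1–2 events

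*Combined protocol and SAP*

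**What the plan says.** Three sentences in the combined protocol and SAP set the rule for entering adverse events in the study database.

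- Section 7.4: "All grade 3 and above adverse events will be entered into OnCore", irrespective of attribution.
- Appendix 4, section 3.1: "All Grade 3-5 Adverse Events (AEs), regardless of being unexpected or considered to be associated with the use of the study drug will be entered".
- Section 7.6: "All adverse events, whether or not unexpected, and whether or not considered to be associated with the use of the study drug, will be entered". This sentence then refers back to the preceding text, and the section closes by pointing to Appendix 4 for the detailed monitoring plan.

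For serious events there is a separate rule with no grade limit, in Appendix 4, section 3.2: "All Serious Adverse Events are entered into OnCore".

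OnCore is the only study database described. Section 9.6 states "All study data will be entered into OnCore" by way of the CRFs, and section 8.3.3 builds the adverse event tables from terms recorded on the CRFs. Section 2.4.2 lists nine safety endpoints, which section 8.3.3 repeats as tables. Section 8.4 adds frequencies of drug-related toxicities without restricting them by grade.

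**The concern.** A site that looks up what to record will go first to section 7.4, which gives a Grade 3 threshold. The all-grade sentence in 7.6 does not settle the matter, because both of its cross-references lead back to the narrower rule: the text above it is 7.4, and Appendix 4 repeats Grade 3–5. Section 8.2.3 names three accruing centers, so practice could differ between them.

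If the narrower rule were followed, non-serious Grade 1–2 events could be left out of OnCore. Several planned safety tables would then be incomplete, and a dose hold, reduction or stop prompted by a low-grade event might have no adverse event record behind it. Low-grade events that were not entered prospectively are hard to recover later.

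**Working it through.** No sample size, power or error rate is involved. The check sets the passages side by side and counts.

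**Step 1. Which events each rule covers**

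| Event | 7.4 and Appendix 4 s3.1 | Appendix 4 s3.2 | 7.6 |
|---|---|---|---|
| Grade 3–5 | entered | entered if serious | entered |
| Grade 1–2, serious | not named | entered | entered |
| Grade 1–2, non-serious | not named | not named | entered |

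The rules differ in effect only in the last row.

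**Step 2. Which safety endpoints draw on that row (section 2.4.2)**

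| Endpoint (paraphrased) | Can include non-serious Grade 1–2? |
|---|---|
| All TEAEs | Yes |
| TEAEs by grade | Yes |
| Grade 3+ TEAEs | No |
| Drug-related TEAEs | Yes, no grade limit |
| Dose-limiting toxicities | Cannot be classed; the term is not defined |
| Serious TEAEs | No |
| Fatal TEAEs | No |
| TEAEs leading to discontinuation | Yes |
| TEAEs leading to interruption, reduction or delay | Yes |

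Count: 5 yes + 3 no + 1 undefined = 9. It would be 6 of 9 if dose-limiting toxicity were defined to include such events. The items overlap, so 5 of 9 is not a share of data lost.

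**Step 3. Can a Grade 1–2 event lead to a dosing action here?**

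The tables in section 5.2 that set dosing actions are 5.3 and 5.5 to 5.15, which is 1 + 11 = 12. The following can hold, reduce or stop drug at Grade 1 and/or 2:

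- 5.3: Grade 2 events in general
- 5.5: Grade 1 and 2 rash
- 5.6: persistent Grade 2 diarrhea
- 5.10: Grade 2 pneumonitis
- 5.11: Grade 1 and 2 visual changes
- 5.13: Grade 2 liver chemistry elevation
- 5.14: treatment-related ILD or pneumonitis of any grade
- 5.15: Grade 1 and 2 bradycardia

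That is 8 of 12 (8/12 = 67%). Permanent discontinuation is among the actions, in 5.10 (Grade 2 pneumonitis that does not recover) and in 5.14. These rows are cited only as examples; no position is taken on their content.

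The four tables not counted:

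- 5.7 (asymptomatic row) and 5.8 act on LVEF or blood pressure and symptoms, not on a stated Grade 1–2.
- 5.9 acts at QTcB of 501 msec or more, which 5.14 labels Grade 3.
- 5.12 acts on Grade 2–3 RPED, which 5.11 has reported as an SAE and which is therefore entered in any case.

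**Step 4. What cannot be computed**

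The documents give no Grade 1–2 split for this population, so the number of events at risk cannot be estimated.

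**The case against.** The strongest reply is that the three sentences can all be obeyed at once. Entering every event satisfies a rule to enter Grade 3 and above, neither narrower sentence contains the word *only*, and omitting Grade 1–2 events would breach 7.6.

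Other text also leans towards full capture. Section 7.4 itself says "Signs or symptoms reported as adverse events will be graded and recorded by the Investigator according to the CTCAE" and defines Grades 1 and 2. Both 7.6 and Appendix 4 provide for review of all entered events separately from Grade 3–5 events: the Site Committee is to "review and discuss at each weekly meeting the selected toxicity, the toxicity grade, and the attribution" under 7.6, and under Appendix 4 entered events "will be reviewed on a monthly basis at the UCSF Coordinating Center Site Committee meetings". Appendix 4 also has participating sites report clinically significant events to the Coordinating Center, which might pick up some events behind a dose change. The harm depends on CRFs that are not in the documents.

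Much of this stands. All-grade capture was probably intended, and loss of data is not shown. It does not remove the defect. If every event is to be entered, a Grade 3 threshold in an entry sentence has no function, yet it is stated twice. The sentence on grading and recording does not say where the record is kept, and the report of clinically significant events is not a database entry rule.

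It is also fair to say that the 8-of-12 table count does not measure data at risk. It shows only that low-grade events can affect dosing in this trial. Without the SAE exclusion, Table 5.12 would make it 9.

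A last objection is that all-grade entry sends more events into a review that is weekly in 7.6 and monthly in Appendix 4. That mismatch exists already and can be reconciled separately.

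**Conclusion.** The concern holds. Sections 7.4 and 7.6 and Appendix 4 section 3.1 give different entry rules with no order of precedence, and the narrower rule would not support five of the nine safety endpoints or the drug-related frequencies in section 8.4.

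The conclusion rests on two readings: that OnCore is the sole source for the safety tables (sections 8.3.3 and 9.6), and that a site could reasonably act on 7.4 and Appendix 4 as they stand. Whether any site would do so cannot be told from the documents.

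The consequence is bounded. Section 8.2.1 makes the safety analyses descriptive, and the primary response endpoint, Grade 3+ events and SAE reporting are untouched. Because safety and tolerability is a stated secondary objective (section 2.2), the wording should be corrected, but the point does not threaten the trial's main conclusion.

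**What to change.** In the entry sentences of section 7.4 and Appendix 4 section 3.1, replace the Grade 3 threshold with all grades (1–5), regardless of attribution, so that both match section 7.6 and the endpoints in 2.4.2. Add no new time window to the entry rule. Leave SAE reporting and the committee review provisions as they are.

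The cost is a protocol amendment, which section 9.4 requires the PRC and IRB to approve; extra data entry for about 27 patients; and Grade 1–2 events passing through the existing Site Committee review. No new assessments are needed, because Table 6.1 already schedules adverse event assessment at visits.

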## 7.5 Follow-up of Adverse Events

All adverse events will be followed with appropriate medical management until resolved. Patients removed from study for unacceptable adverse events will be followed until resolution or stabilization of the adverse event. For selected adverse events for which administration of the investigational drug was stopped, a re-challenge of the subject with the investigational drug may be conducted if considered both safe and ethical by the Investigator.

## 7.6 Adverse Events Monitoring

All adverse events, whether or not unexpected, and whether or not considered to be associated with the use of the study drug, will be entered into OnCore®, as noted above.

The Investigator will assess all adverse events and determine reportability requirements to the UCSF Data and Safety Monitoring Committee (DSMC) and UCSF's Institutional Review Board (IRB); and, when the study is conducted under an Investigational New Drug Application (IND), to the Food and Drug Administration (FDA) if it meets the FDA reporting criteria.

All adverse events entered into OnCore® will be reviewed by the Helen Diller Family

Comprehensive Cancer Center Site Committee on a weekly basis. The Site Committee will

review and discuss at each weekly meeting the selected toxicity, the toxicity grade, and the attribution of relationship of the adverse event to the administration of the study drug(s).

All grade(s) 3-5 adverse events entered into OnCore® will be reviewed on a monthly basis at the Site Committee meetings. The Site Committee will review and discuss the selected toxicity, the toxicity grade, and the attribution of relationship of the adverse event to the administration of the study drug(s).

In addition, all suspected adverse reactions considered "serious" entered into OnCore®, will be reviewed and monitored by the Data and Safety Monitoring Committee on an ongoing basis and

discussed at DSMC meetings, which take place every six weeks.

For a detailed description of the Data and Safety Monitoring Plan for a Multicenter Phase 2 or 3 Institutional Study at the Helen Diller Comprehensive Cancer Center please refer Appendix 4 Multicenter Institutional Studies.

